14.4 Costs to Participants

There will be no costs to the study participants for participation. The sponsor will cover all direct costs of study procedures required for participation, including any assessments or tests performed solely for the purpose of establishing eligibility for participation. Charges for treatment of a participant's condition that are unrelated to the research study or any unrelated procedures will not be covered by the sponsor. Patients who previously received therapy from a therapy team member prior to the study, and who will continue to receive ongoing treatment outside of the study from that therapist, are responsible for those non-study related costs. Participants may be reimbursed for reasonable expenses incurred for study participation, such as local travel to the treatment site; this will be specified in each site's ICF.

14.5 Treatment and Compensation for Study Related Injury

If a participant becomes sick or injured during the study, they should call the site physician. Some study-related emergencies can be treated by the site physicians. If the site physicians cannot treat a study-related emergency, then there are contingency plans for the transport of participants to the nearest hospital.

Treatment of a study-related injury, sickness, or emergency would first be billed to a participant's health insurance provider, if the participant has health insurance. If the participant's private or employer health insurance plan does not cover clinical trial-related claims that occurred during the course of the study, then the sponsor will cover any treatment costs directly related to the study. To cover these costs, the sponsor carries third-party insurance.

The sponsor will not cover costs of ongoing treatment unrelated to the study due to pre-existing conditions, or the cost of the participant's time spent obtaining treatment for pre-existing conditions before receiving treatment in the study.

14.6 Record Retention

Investigators must retain all study records required by the sponsor and applicable ICH-GCP and FDA regulations, and Health Canada Guidance for Records Related to Clinical Trials (GUIDE-0068) in a secure and safe facility. The investigator must consult a representative of the sponsor before disposal of any study records. "Essential documents" are defined as documents that individually and collectively permit evaluation of the conduct of a trial and the quality of the data produced. These documents will be filed according to ICH-GCP regulations in the ISF. It is the responsibility of the sponsor to inform the investigator or institution when these documents no longer need to be retained.

14.7 Publication Policy

The sponsor recognizes the importance of communicating medical research and scientific data and their obligations to participants enrolled in a study and therefore, encourage publication of such material in reputable scientific journals and at professional and/or academic seminars or conferences. For multicenter studies, it is intended that the first publication of the study's primary clinical data be co-authored by designated participating centers and the sponsor or designated representatives. Inclusion of Clinical Investigators in the authorship of any multi-center publication will be based upon substantial contribution to the design, analysis, interpretation of data, drafting and/or critically revising any manuscript(s) derived from the Study. All publications will follow ICMJE Recommendations for the Conduct, Reporting, Editing, and Publication of Scholarly Work in Medical Journals, unless other guidelines are required by the journal. It is understood by the Clinical Investigators that the information generated in this study will be used by the sponsor in connection with the development of the IMP and therefore may be disclosed to government agencies in various countries. To allow for the use of information derived from the study, it is understood that the investigators are obliged to provide the sponsor with complete test results, all study data, and access to all study records. It is mandatory that all data analysis is done on the official monitored sponsor database and that the analysis plan is agreed upon with the sponsor statistician.

Any results of medical investigations with the sponsor and/or publication/lecture/manuscripts based thereon shall be exchanged and discussed by the investigator and sponsor prior to submission for publication or presentation. Due regard shall be given to the sponsor's legitimate interests, e.g., manuscript authorship, obtaining optimal patient protection, coordinating and maintaining submissions to health authorities, and coordinating with other ongoing studies in the same field. The full details of the processes of producing and reviewing reports, manuscripts, and presentations based on the data from this trial will be described in the Clinical Trial Agreement.

15.0 Appendix A: Sub-study without Overnight Stays

Rationale

This sub-study to the MAPPUSX protocol "A Multi-Site Open-Label Safety Extension Study of Manualized MDMA-Assisted Therapy for the Treatment of Participants with Posttraumatic Stress Disorder" allows participants to be discharged in the evening after the Experimental Session is over at select investigational study sites. In MAPS' Phase 2 study MAA1, which tested the safety and efficacy of MDMA-assisted therapy for social anxiety among autistic adults, an overnight stay was not required. This approach was also tested in the Phase 2 study MP16 and Phase 3 study MAPP1 with no safety concerns due to travel to home or hotel; this approach was found to be comparable in safety to participants who had an overnight stay. The sub-study has also been tested in the Phase 3 study MAPP2. The accumulation of these sub-study samples will enable a sample size to permit an integrated analysis of safety for this protocol variant compared to participants with an overnight stay.

MAPPUSX Protocol

Amendment 3 Version 1: 15 March 2023

Study site and participants will follow all protocol procedures described in the main protocol, except those related to overnight stays as described below. The overnight stay is included in the main study protocol primarily as an opportunity for rest and integration in a relaxed and comfortable environment away from the distractions of home, and to facilitate the logistics of participation in the integrative visit at the site on the day following the Experimental Session. The overnight stay is not required for medical reasons, but in case of emergencies, the therapists and study physician are on-call for all sites.

In the main study protocol, a Night Attendant accompanies the participant during the overnight stay. The Night Attendant's primary function is to ensure the participant is comfortable and has a meal, to provide minimal support, and to alert qualified site staff in case of need expressed by the participant or determined by observation. All Night Attendants are interviewed, trained, and approved by therapy teams to ensure they are comfortable providing the necessary support and know whom to call if medical support is needed from the therapy pair or study physician.

Medically-trained Night Attendants have not been required for any of the five Phase 2 studies of MDMA-assisted therapy for PTSD since MP-1 was completed. In MP-1, the first Phase 2 study, the FDA required that the Night Attendant be a registered nurse. Since MP-1, Night Attendants were not required to have medical training in subsequent studies. Among 189 participants treated under this IND, no medical complications have arisen during overnight stays under the watch of Night Attendants.

The sponsor and investigators agree that allowing participants who are screened for stable domestic circumstances to return home will not increase the risks of participation in the study. The study protocol discusses the risk of psychological distress in a PTSD population and mitigation in Section 9.2.2.2
Psychological Risks and Mitigation. Therapists and site physicians are aware of these risks, including anxiety and depressed mood occasionally reported 1 to 3 days after MDMA administration. In previous Phase 1 and 2 studies, these reactions have been transient and have responded well to reassurance from the therapy pair, with occasional use of benzodiazepines for anxiety. If needed, the study physician may prescribe a short-acting, low-dose benzodiazepine (specifically, lorazepam) or sleep aids (excluding trazodone) as needed.

Consistent with the main study protocol and the sub-study, proper preparation and follow-up support will reduce the difficulties participants might have with acute or sub-acute reactions. The potential for destabilizing psychological distress will be minimized by:

• Excluding people who might be more vulnerable to it (such as people diagnosed with bipolar affective disorder type 1 or with psychotic disorders).

- MAPPUSX Protocol Amendment 3 Version 1: 15 March 2023
- Excluding people who do not have a stable living situation or supportive family/network.
- Preparatory Sessions of non-drug therapy before the Experimental Session.
- Creating an atmosphere of trust during the Experimental Session.
- Close monitoring.
- Phone contact with participants during the week after the Experimental Session.
- Conduct of Integrative Session on the morning after the Experimental Session.

Specific to sub-study:

- Therapist phone contact with participants on the night of the Experimental Session.
- A support person identified by the participant and agreed upon by the therapist must stay with the participant overnight on the evening following the Experimental Session.
- The therapists will meet with the support person prior to the first Experimental Session to assess their ability to act as an appropriate support person and to give them instructions about what to expect following Experimental Sessions and how to contact study personnel if needed.
- A support person must assist the participant during transfer from study site after the Experimental Session and to the study site on the following morning for the Integrative Session. This Integrative Session will start later in the day to allow for logistics of transportation. Participants can arrange their own transportation after the Integrative Session. The Integrative Session may happen remotely if approved by the research team.

Implementation of Sub-study

All eligibility criteria from the main study protocol will apply, except for the following inclusion criteria listed as a Lifestyle Modification:

Post Experimental Session

- Are willing to remain overnight at the study site after each Experimental Session until after the Integrative Session the next morning (for exceptions see Appendix A sub-study)
- Agree not to drive after the Experimental Sessions until after the Integrative Session the next morning.

Sub-study participants will be required to be willing to:

Post Experimental Session

- Identify a support person willing to accompany them overnight at a safe location of their choice after each Experimental Session.
- Have the support person escort them away from the study site in the evening after the Experimental Sessions and to the site on the following morning for the Integrative Session. The Integrative Session may happen remotely if approved by the research team.

Screening & Preparatory Periods

During the Screening and Preparatory Period, the participant will identify an appropriate support person to stay with the participant on the evening of the Experimental Session. Participants will be escorted to and from the study site after Experimental Sessions. The support person is not required to be the same as the escort for the participant. There may be more than one support person(s), and they will be responsible for providing companionship as needed overnight and contacting the study team with any questions or concerns. Any support person spending the night with the participant will meet the therapy pair, during the Preparatory Period or in advance of the appropriate Experimental Session in-person to be oriented to

the role. An escort who is responsible only for transportation need not meet with the therapy pair to perform that role. The participant will provide contact information for the appropriate support person(s) in advance of each Experimental Session.

Orienting the Support Person

In advance of the appropriate Experimental Session, the support person staying with the participant overnight will be required to meet with the therapy pair in person. The support person will receive printed instructions, including contact information of the study physician, therapists, investigator, and Study Coordinator and what to do in the case of an emergency.

The support person will not provide therapy to the participant. Minimal discussion is acceptable, but only if initiated by the participant. The support person should not interpret the participant's experience or act as therapist. The therapy pair will discuss this explicitly with the support person and include this information in the written instructions.

The main roles of the support person include:

- Ensuring the participant has a comfortable place to sleep and discuss the plan for wakeup, breakfast, and travel time for the next day's Integrative Session.
- Seeing to the participant's needs for food and liquids, including providing dinner and breakfast in accordance with the participant's dietary preferences.
- Eating with the participant unless they ask to be left alone.
- Cleaning up after the participant, including doing the dishes and handling bedding
- Keeping all participant information confidential.
- Ensuring the participant is safely transported to and from the study site as appropriate (may be completed by a separate support person).
- Ensuring that the participant does not leave the overnight site without accompaniment and does not leave the participant alone at the overnight site. The participant may have privacy at the overnight site.
- Supervising the participant to ensure they do not consume drugs or alcohol on the night of the Experimental Session and that phone/computer time is limited.
- Remaining sober throughout the entire overnight stay.
- Remaining available to participant's needs throughout the night, but may sleep if the participant is sleeping.

End of Experimental Sessions

Consistent with the main protocol, at the end of each Experimental Session, the therapy pair and site physician will assess the participant to decide if they are physically and emotionally stable. If the participant is not stable, the therapy pair and/or site physician will stay with the participant until stable or escalate for further care as appropriate. If it is in the best interest of the participant for them to spend the night at the study site, the therapists will ensure an appropriate stay is provided.

In the sub-study, if a participant is deemed medically and psychologically stable by the therapy pair at the end of the Experimental Session, the participant will be escorted home via car, rideshare, or public transportation and will not remain overnight at the study site. The support person will be provided with an instruction sheet including how to contact the Clinical Investigator, Site Physician, and/or therapy pair to report any issues. The support person will stay overnight with the participant and be instructed to call 911 in the case of a psychiatric or medical emergency.

Each participant will be instructed to call the therapy pair when they arrive where they will stay for the night. If the therapy pair has not received a call within 2 hours after the participant has left the site, the therapists will call the participant and support person to confirm arrival. The therapy pair will ask about the participant's emotional well-being and invite them to begin the process of integration through self-reflection, journaling, meditation, or other quiet activities. The therapy pair will remind the participants that this evening should be an opportunity to rest and integrate and that they should avoid unnecessary stresses, chores, etc. The therapy pair will also discuss this with the participant during the Preparatory and Experimental Sessions. The therapy pair and site physician will remain on-call overnight to attend to any medical or psychological issues that may come up for the participant.

In the sub-study, if a participant is deemed to be not psychologically stable at the end of the Experimental Session, they will remain under the care of their therapy pair. The therapy pair will continue to evaluate the participant to make further disposition recommendations depending on the participant's psychological condition. This could include: continued observation, psychological support and/or psychopharmacologic interventions; or further evaluation for potential transfer as appropriate per site Standard Operating Procedures (SOPs). If the therapy pair determines that the participant needs ongoing observation and psychological care at the same location as the Experimental Session, there will be the option for them to remain overnight with the therapy pair in accordance with site SOPs. If the participant will not be leaving the site for the night, the therapy pair will call the support person(s) to inform them and arrange appropriate transportation following the Integrative Session on the following day if appropriate.

Sub-Study Objective & Evaluation

The primary objective of this sub-study will be to evaluate the feasibility of conducting MDMA-assisted therapy for PTSD among participants who do not remain at the study site overnight after Experimental Sessions.

This sub-study will include all participants enrolled and treated at select study sites. No formal analysis is planned to support this objective due to small sample size. However, case reports and AEs collected on the night of the Experimental Session will be evaluated to support feasibility. These reports will be used to explore feasibility of expanding the sub-study to include additional clinical sites and to support generalizability of potentially delivering this treatment to varied treatment settings post-approval.

References

- 1. Yehuda, R., et al., *Post-traumatic stress disorder*. Nat Rev Dis Primers, 2015. 1: p. 15057.
- 2. APA, Clinical practice guideline for the treatment of posttraumatic stress disorder (PTSD) in adults. 2017.
- 3. Burg, M.M. and R. Soufer, *Post-traumatic Stress Disorder and Cardiovascular Disease*. Curr Cardiol Rep, 2016. **18**(10): p. 94.
- 4. Koenen, K.C., et al., *Posttraumatic stress disorder in the World Mental Health Surveys.* Psychol Med, 2017. **47**(13): p. 2260-2274.
- 5. Nichter, B., et al., *Psychological burden of PTSD, depression, and their comorbidity in the U.S. veteran population: Suicidality, functioning, and service utilization.* J Affect Disord, 2019. **256**: p. 633-640.
- 6. Lamarche, L.J. and J. De Koninck, *Sleep disturbance in adults with posttraumatic stress disorder: a review.* J Clin Psychiatry, 2007. **68**(8): p. 1257-70.
- 7. Lanius, R.A., et al., *The dissociative subtype of posttraumatic stress disorder: rationale, clinical and neurobiological evidence, and implications.* Depress Anxiety, 2012. **29**(8): p. 701-8.
- 8. Lanius, R.A., et al., *Emotion modulation in PTSD: Clinical and neurobiological evidence for a dissociative subtype.* Am J Psychiatry, 2010. **167**(6): p. 640-7.
- 9. Nicholson, A.A., et al., *The Dissociative Subtype of Posttraumatic Stress Disorder: Unique Resting-State Functional Connectivity of Basolateral and Centromedial Amygdala Complexes.* Neuropsychopharmacology, 2015. **40**(10): p. 2317-26.
- 10. Hoge, C.W., et al., *Combat duty in Iraq and Afghanistan, mental health problems, and barriers to care.* N Engl J Med, 2004. **351**(1): p. 13-22.
- 11. Statement Of Jon A. Wooditch Acting Inspector General Department Of Veterans Affairs, in Committee On Veterans' Affairs Subcommittee On Disability Assistance And Memorial Affairs. 2005: Washington, DC.

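### The no-overnight sub-study's objective and inclusion rule name different groups, and neither document counts sessions where a planned evening discharge did not happen

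*Protocol*

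**What the plan says.** All the relevant text is in protocol section 15.0, Appendix A.

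- **Objective (Sub-Study Objective & Evaluation):** to "evaluate the feasibility of conducting MDMA-assisted therapy for PTSD among participants who do not remain at the study site overnight after Experimental Sessions".
- **Inclusion (next paragraph):** "This sub-study will include all participants enrolled and treated at select study sites". Nothing here depends on where the night was spent.
- **Evidence:** "No formal analysis is planned to support this objective due to small sample size"; instead, "case reports and AEs collected on the night of the Experimental Session will be evaluated to support feasibility". The reports are to inform expansion to more sites and delivery in varied settings after approval.
- **End of Experimental Sessions:** a participant judged medically and psychologically stable is escorted home. However, "if a participant is deemed to be not psychologically stable at the end of the Experimental Session, they will remain under the care of their" therapists, with further observation, support, medication or transfer all possible. If continued care on site is needed, "there will be the option for them to remain overnight with the therapy pair in accordance with site SOPs". A separate sentence allows a night on site where that is in the participant's best interest.
- **Rationale:** data from several trials' sub-studies are being accumulated to "permit an integrated analysis of safety for this protocol variant compared to participants with an overnight stay".

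SAP section 2.0 mentions the sub-study in one sentence. SAP section 8.1 defines only the Safety and All Enrolled sets. Neither document gives a feasibility endpoint, denominator or success criterion, or a count of unplanned overnight stays.

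**The concern.** Whether a participant goes home is decided at the end of the session, after dosing, and partly on how the session went. An objective confined to those who do not stay overnight, if taken literally, conditions on the success it is meant to assess. The inclusion rule does not repeat that restriction, so the two statements describe different groups. Neither picks out the sessions that matter for feasibility, which are those that began with evening discharge planned.

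None of the listed evidence is a tally of failed discharges. An AE records distress, not that the participant could not leave, and a best-interest stay need not produce an AE or a case report. A favourable feasibility statement could therefore be written without a reader learning how often the model broke down. That statement is intended to support wider use, and the same data feed a pooled safety comparison in which the grouping of retained participants is not stated.

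**Working it through.** There is no planned figure to reproduce: the sub-study has no sample size, rate, threshold or interval. The check is mainly textual.

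**Which sessions each wording covers**

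- *Objective, read literally:* sessions after which the participant left. Sessions ending in an overnight stay on site are outside it.
- *Inclusion rule:* all sessions of all participants treated at the selected sites. Retained sessions are inside it. So are any sessions where an overnight stay was planned from the start, since Appendix A permits evening discharge rather than requiring it.
- *Set needed for feasibility:* sessions that began with evening discharge planned. Neither wording identifies this set.

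**Whether a failed discharge reaches the stated evidence**

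- It can. Protocol section 7.3.1 has AEs recorded at session end, and section 10.1.1 defines AEs very broadly.
- It need not. No field, count or table is specified for it. Protocol Table 5 and SAP Table 2 list a potential overnight stay at Visits 4, 8 and 12, but do not separate planned from unplanned stays.

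**Illustration of size (every rate and sample size is an assumption)**

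1. *Per session.* Take 10 participants with 3 sessions each, so 30 sessions.
   - 3 held back: 27/30 = 90.0% discharged (exact 95% CI 73.5% to 97.9%).
   - 6 held back: 24/30 = 80.0% (61.4% to 92.3%).
   - Restricted to sessions where the participant left: 27/27 or 24/24 = 100% by construction.
   - These intervals treat sessions as independent and are indicative only.
2. *Chance of at least one held-back session* at a true 10% rate, 1 − 0.90^s: 0.79 for s = 15, 0.96 for s = 30, 0.998 for s = 60. At that rate, even a small sub-study would probably contain one.
3. *Per participant.* With hold-back rate q per session and independent sessions, P(at least one in three) = 1 − (1 − q)³:
   - q = 5%: 1 − 0.8574 = 14.3%
   - q = 10%: 1 − 0.7290 = 27.1%
   - q = 15%: 1 − 0.6141 = 38.6%
   - If the same people tend to be held back each time, the share is lower, down to q itself.
4. *Night AEs.* Assume a rate of 30% in held-back sessions, 5% in the rest, and 10% held back. By planned disposition: 0.10 × 30% + 0.90 × 5% = 7.5%. Among those who left: 5.0%, lower by 2.5/7.5 = one third. This gap arises only if held-back sessions are dropped or moved to another group.

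**The case against.** The paragraph after the objective keeps retained participants in the sub-study, and its AEs and case reports are not limited to those who went home. Distress serious enough to stop discharge would normally be recorded as an AE that evening and is an obvious subject for a case report. The objective's phrase can also be read as naming the protocol variant rather than a denominator. With no formal analysis, there is no denominator from which sessions are removed. An unstable participant may stabilise and leave, so instability at session end is not the same as a night on site. The rates above have no source in the documents, and the sponsor chose a descriptive evaluation because numbers are small.

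Most of this stands, and it rules out three stronger readings:

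- *That a failed discharge can never count against feasibility.* The inclusion rule and the unrestricted evidence contradict this.
- *That the result is favourable by construction.* That would follow only if the objective's literal restriction were applied, and the next paragraph does not apply it.
- *That the pooled safety comparison is biased toward home discharge.* The Rationale does not say how participants will be grouped. Bias in that direction would arise if they were grouped by where the night was actually spent and held-back participants had more night AEs.

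The objection does not show that failed discharges will be reported. Small numbers are a reason to avoid formal testing, but not to omit a simple count.

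**Conclusion.** The point holds as a mismatch of wording and a missing measure. Objective and inclusion rule do not name the same group, and failed discharge is neither an outcome nor a count in either document, so feasibility could be declared without disclosing it. The documents do not allow the effect to be sized. At assumed hold-back rates of 10% or 20% in 30 sessions, the undisclosed quantity would be the gap between 90% or 80% and 100%. The per-participant figures also assume independent sessions, and the AE example rests on assumed risks.

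Severity is low. The sub-study is descriptive, and neither the primary PCL-5 analysis nor the Safety set, which includes everyone who receives study drug, is affected. It is still worth correcting, because this is the sub-study's primary objective and its data are meant for pooling.

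**What to change.** In Appendix A, with a matching short paragraph in the SAP:

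1. Reword the objective to cover all Experimental Sessions at sub-study sites that start with same-evening discharge planned.
2. Record planned and actual overnight disposition for each session.
3. Report descriptively the number and proportion of planned-discharge sessions that ended in discharge, with reasons where they did not (kept on site or transferred), and the number of participants with at least one such failure. If an interval is given, calculate it at participant level or allow for repeated sessions per participant.
4. Tabulate night-of-session AEs by planned disposition.
5. State that data go to the integrated safety comparison with planned disposition identified, so that retained participants are not moved into the overnight comparator.

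No clinical rule changes. The cost is some wording and one planned/actual record per session. Sites already make this decision, and they call the support person when a participant stays. The downside is that reported feasibility may look less favourable.
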